6.1.4. Study Drug Preparation

Once at the investigational site and/or with the patient/caregiver, ataluren sachets should be stored at room temperature, away from the reach of children, until the time of reconstitution. The appropriate sachet strength will be used to prepare each dose. The full contents of each sachet should be mixed with at least 30 mL (1 ounce) of liquid, or 3 tablespoons of semi-solid

food. The prepared dose should be mixed well before administration. The amount of the liquid or semi-solid food can be increased based on patient preference.

Each prepared dose is best administered immediately after preparation. The prepared dose should be discarded if not consumed within 3 hours (if kept at room temperature) or within 24 hours of preparation (if kept refrigerated).

Detailed written drug mixing and dosing instructions will be provided to the patient/caregiver when ataluren supplies are dispensed. A copy of these instructions will be maintained in the Investigator site study file.

6.1.5. Study Drug Accountability

The Investigator and/or the responsible site personnel must maintain accurate records of the receipt of all ataluren shipped by PTC Therapeutics or its designee, including, but not limited to, the date received, lot number, amount received, and the disposition of all ataluren. Current reconciliation and dispensing records must also be maintained that include the date and amount of ataluren dispensed, relevant batch numbers, and patient's assigned study number. Caregivers should return all unused sachets of ataluren to the investigational site at the end of each 12-week treatment interval for inventory. The eCRF will serve as the source document for drug supply to the patients and will document the return of any unused drug for compliance assessments.

Depending upon the decision of PTC Therapeutics, unused clinical supplies must be destroyed or returned to PTC Therapeutics (or its designee) after the study is completed and drug accountability has been verified by the monitor. Records documenting the date of study drug destruction or shipping, relevant batch numbers, and amount destroyed or shipped should be kept in the investigational site study file.

The Medrio EDC system will be used to track drug accountability.

6.1.6. Overdose Precautions

For any patient experiencing an overdose (see [Section 9.1.1](#) for the definition of overdose), observation for any symptomatic side effects should be instituted, and vital signs and biochemical and hematological parameters should be followed closely (consistent with the protocol or more frequently, as needed). Appropriate supportive management to mitigate adverse effects should be initiated. Pending the acquisition of sufficient human experience with the drug, use of gastric lavage or induction of emesis is not specifically recommended or contraindicated.

The PTC Therapeutics medical monitor must be contacted if an overdose occurs. Under applicable regulations, overdosing may be considered a SAE and should be reported accordingly (see [Sections 9.1.1](#) and [9.1.2](#)).

6.1.7. Inadvertent Exposure and Spill Precautions

Based on available data from nonclinical studies, ataluren does not appear to be acutely toxic or genotoxic at levels that are likely to result from inadvertent exposure to the contents of the packet, if opened. Based on general experience with the drug during manufacturing, it does not appear that exposure to formulated ataluren is likely to be irritating to skin or eyes. However, personnel handling the drug should use reasonable precautions to avoid eye contact, skin contact,

inhalation, or ingestion of the material in the packets. Refer to the Ataluren IB for current information on inadvertent exposures and spill precautions.

6.2. Study Drug Treatment

6.2.1. Study Drug Dosing

Dosing of ataluren will be based on milligrams of drug per kilogram of patient body weight assessed every 12 weeks. All patients will receive approximately 10, 10, 20 mg/kg ataluren 3 times daily (TID) for 4 weeks during the PK portion and for 48 weeks during the extension period.

6.2.2. Duration of Treatment

The study duration will be 4 weeks during the PK portion and 48 weeks during the extension period (52 weeks total). Initial data assessment and reporting will be after all patients complete first 4 weeks (safety and PK) to satisfy Pediatric Investigation Plan (PIP) requirements and an additional report will be issued after completion of 48 weeks extension). The study may be terminated by the sponsor at any time and for any reason, eg, the clinical development of ataluren in dystrophinopathy is discontinued.

6.2.3. Schedule of Administration

As noted in [Table 1](#), 3 doses should be taken per day – the 1st dose in the morning, the 2nd dose during the middle of the day (midday), and the 3rd dose in the evening. Intervals for dosing should be ~6 hours (± 1 hour) between morning and midday doses, ~6 hours (± 1 hour) between midday and evening doses, and ~12 hours (± 1 hour) between evening doses and the morning dose on the next day.

Table 1: Suggested Daily Dosing Schedule

Dose Designation	Example Dosing Times
Morning	~7:00 AM – 0700 hours (± 1 hour)
	↑ ~6 hours ↓
Mid-day	~1:00 PM – 1300 hours (± 1 hour)
	↑ ~6 hours ↓
Evening	~7:00 PM – 1900 hours (± 1 hour)
	↑ ~12 hours ↓
Next Day Morning	7:00 AM – 0700 hours (± 1 hour)

6.2.4. Instructions for Delays in Dosing

Dosing delays should be handled as follows:

- If there is a delay in the administration of ataluren of **<3 hours** after the morning or midday doses or **<6 hours** after the evening dose, the planned dose should be taken with no changes to the subsequent dose schedules.
- If there is a delay in the administration of ataluren of **>3 hours** after the morning or midday doses or **>6 hours** after the evening dose, the planned dose should **not** be taken and patients should resume their usual dosing schedule.

6.3. Safety Monitoring and Study Drug Dose Interruption/Modification

6.3.1. Laboratory Abnormalities and Adverse Events Requiring Evaluation and Potential Drug Interruption/Modification

Patients must be monitored closely for AEs or laboratory abnormalities during the course of the study.

For AEs or laboratory abnormalities, the Investigator will use judgment in determining whether the event or abnormality is clinically significant, whether diagnostic evaluation is warranted, and whether potential interruption of study drug treatment is appropriate. In general, life-threatening (Grade 4) or severe (Grade 3) AEs or laboratory abnormalities should be considered clinically significant, although recurrent or persistent moderate events (Grade 2) may also be considered clinically significant in certain circumstances. Reference should be made to the Common Terminology Criteria for Adverse Events (CTCAE), Version 4.0 (see http://evs.nci.nih.gov/ftp1/CTCAE/CTCAE_4.03_2010-06-14_QuickReference_5x7.pdf) for grading the severity of AEs and laboratory abnormalities.

6.3.2. Evaluation of Adverse Events or Laboratory Abnormalities

While specific monitoring, diagnostic testing, and supportive care measures must be instituted based on the clinical judgment of the Investigator, Investigators are encouraged to contact either the PTC Therapeutics medical monitor (or designee) to obtain guidance and to ascertain whether similar events are being seen at other investigational sites. The PTC Therapeutics medical monitor should be notified of any AE or laboratory abnormality that leads to dose interruption and should be apprised of ancillary laboratory or other diagnostic findings and the evolving data from any work-up of the initial abnormality. The PTC Therapeutics medical monitor may suggest review of the case with gastroenterology or nephrology consultants or with other experts (either at the site or retained by PTC Therapeutics).

Clinical evaluations for potential hepatic and renal toxicities may include the following:

- **Hepatic:** The medical history, hepatitis screening results, all clinical blood values (particularly serum bilirubin, gamma-glutamyl transferase [GGT], aspartate aminotransferase [AST], and alanine aminotransferase [ALT] values), and all concomitant medications should be reviewed. Depending upon changes observed, the recommended diagnostic workup may include more frequent monitoring or further evaluations for viral hepatitis and immune disorders; tests for cholelithiasis; or abdominal ultrasound, computed tomography (CT), magnetic resonance imaging (MRI), or other imaging methods.
- **Renal:** The medical history, all clinical blood and urine renal values, serum electrolytes, medications, and potential pre- or post renal conditions should be reviewed. Depending upon the changes observed, recommended diagnostic workup may include further evaluations of blood or urine; tests of glomerular filtration rate (GFR), concentrating ability, or other renal functions; CT, MRI, or other imaging methods; and/or renal biopsy. Transient reversible mild (Grade 1) hypercreatinemia was seen in ~15% of patients in Study 009. Therefore, renal function should be monitored and only if sustained (ie, >4 weeks) should dose adjustment or discontinuation be considered after discussion with the PTC Therapeutics medical monitor.

6.3.3. Instructions for Resuming Study Drug Administration after an Interruption for Safety Concerns

In deciding whether to re-institute study drug after a dose interruption for any clinically significant safety concern, the Investigator in consultation with PTC Therapeutics should consider factors such as the following:

- Type and severity of the AE or laboratory abnormality
- The potential causal relationship of study drug
- The patient's status in terms of dystrophinopathy and other health conditions
- The ability to monitor for recurrence of the event

For hepatic or renal events, the level of Investigator certainty that an abnormality leading to drug interruption is drug-related should be considered strongly in deciding if and when to re-institute ataluren treatment. If the Investigator considers the hepatic or renal event that led to ataluren interruption as probably related to ataluren, restarting ataluren is not advised. In this case, the

patient should be discontinued from the study (see [Section 10](#)). If the Investigator considers the hepatic or renal event that prompted ataluren interruption to be possibly related or unlikely related to ataluren, the Investigator should use best judgment in determining whether to restart ataluren. If the hepatic or renal event is considered unrelated to ataluren, re-institution of ataluren is recommended.

If the Investigator believes it is appropriate to do so and the PTC Therapeutics medical monitor has been consulted, ataluren may be re-initiated. If the event was determined to be unrelated to ataluren, the treatment may be resumed at full dose. Otherwise, if the drug is resumed, it should be initially re-initiated at half of the original dose. The appropriate clinic staff should instruct the patient/caregiver about the revised number of study drug sachets to be used per dose according to the new schedule. Re-challenge at half dose should be initiated only as a bridge to full dosing. If a patient cannot tolerate the full dose, he/she should be discontinued from study participation.

If further evaluation reveals that the AE that led to dose reduction was not related to the ataluren, the dose should be escalated to the original dose level.

If after dose reduction, the patient experiences a recurrence of a previous abnormality that led to ataluren dose interruption or experiences a new occurrence of an unacceptable AE or laboratory abnormality, the Investigator should interrupt ataluren and confer with the PTC Therapeutics medical monitor regarding the potential need to discontinue ataluren permanently and discontinue the patient from the study.

6.3.4. Instructions for Discontinuation of Study Drug Administration for Safety Concerns

Study drug should be permanently discontinued following appropriate consideration of study drug interruption/modification and consultation with the PTC Therapeutics medical monitor or designee. If permanent discontinuation of study drug is the result of an SAE, then a follow-up SAE report form must be completed (see [Section 9.7](#)). In the case of treatment discontinuation due to an AE that is not an SAE, the PTC Therapeutics medical monitor or designee should be notified (see [Section 10](#)). In addition, details regarding the reasons for discontinuation and the AEs leading to the discontinuation should be recorded in the source documents and in the appropriate eCRF. The Early Termination (ET) Visit eCRF should be completed and appropriate follow-up (at ~4 weeks post extension period as per protocol or until recovery from or stabilization of the AE, whichever comes last) should be instituted.

7. CONCOMITANT AND SUPPORTIVE THERAPY

7.1. Concomitant Medications

Other than the study drug, any treatments taken by a patient from the screening period through the 4-Week Follow-Up are defined as concomitant medications.

To the extent possible, administration of any treatment other than the study drug should be minimized during the study period. Patients should be discouraged from use of herbal remedies, growth hormone, self-prescribed drugs, street drugs, tobacco products, or alcohol at any time during the study.

If considered necessary for the patient's well-being, drugs for concomitant medical conditions or for symptom management may be given at the discretion of the Investigator. The decision to authorize the use of any other drug(s) should take into account patient safety, the medical need, the potential for drug interactions, the possibility for masking symptoms of a more relevant underlying event, and whether use of a concomitant medication will compromise the outcome or integrity of the study.

Parents/caregivers should be instructed about the importance of informing the clinic staff of the patient's use of any drugs or remedies (whether prescribed, over-the-counter, or illicit) before and during the course of the study. Information regarding all concomitant medications will be collected and documented in the concomitant medication page of the eCRF.

7.1.1. Corticosteroids

To date, corticosteroid use is the only pharmacological intervention that has demonstrated benefit in DMD [[Mendell 1989](#), [Fenichel 1991a](#), [Fenichel 1991b](#), [Griggs 1991](#), [Biggar 2001](#), [Beenakker 2005](#), [Biggar 2006](#), [Pradhan 2006](#)]. Subjects who require corticosteroid interruption, dose modification, or reinstatement may remain on study drug therapy.

Co-administration of systemic corticosteroids with ataluren may cause more frequent instances of hypertension than does systemic corticosteroid use alone (without ataluren). However, the blood pressure data available to date are not definite about any contributory role of ataluren in development of hypertension in patients who are taking corticosteroids.

7.1.2. Nephrotoxic Medications

Renal abnormalities were observed in a Phase 3 trial evaluating ataluren in patients ≥ 6 years of age with nonsense mutation cystic fibrosis (nmCF) who were receiving concomitant IV aminoglycosides and IV vancomycin (as described in the Ataluren IB). Caution should therefore be exercised during concomitant use of study drug and potentially nephrotoxic agents.

In patients who require treatment for serious infections, investigators should substitute other antibiotics for systemic aminoglycosides or vancomycin when clinically appropriate, if possible. If IV aminoglycosides or IV vancomycin are administered, study drug must be interrupted during the course of antibiotic therapy. Patients requiring IV aminoglycoside or vancomycin therapy should be closely monitored in an appropriate setting, such as a hospital. Investigators should be particularly vigilant with patients experiencing nausea, vomiting, diarrhea, fever, or laboratory

evidence of dehydration. Treatment with ataluren may be resumed no earlier than 2 days after administration of these antibiotics has ceased.

In patients receiving such agents, antibiotic drug levels and serum creatinine and blood urea nitrogen (BUN) should be monitored closely as follows:

- Creatinine and BUN should be measured:
 - Prior to initiating IV aminoglycoside or vancomycin therapy
 - Within 24 to 48 hours of the first antibiotic administration (and further antibiotic dosing should be based on these results)
 - At least twice a week during the course of antibiotic treatment (if possible)
- Antibiotic trough levels should be measured:
 - Within 24 to 48 hours of the first antibiotic administration (and further antibiotic dosing should be based on these results)
 - At intervals during the course of antibiotic treatment based on clinical need

7.2. Non-Drug Therapy

7.2.1. Physical Therapy

There are neither restrictions nor prescriptions for physical therapy during the study. Sites should use local best practices in providing physical therapy support for patients participating in the study.

7.2.2. Hydration

Because of the potential risk of renal dysfunction during periods of dehydration in patients receiving ataluren, it is important to encourage study patients to maintain adequate hydration throughout the study. Patients should be adequately hydrated prior to receiving any potentially nephrotoxic agents, and hydration status should be carefully monitored throughout the administration of any agent with nephrotoxic characteristics. Investigators should be particularly vigilant with patients who are experiencing nausea, vomiting, diarrhea, fever, or laboratory evidence of dehydration.

7.2.3. Dietary Restrictions

There are no specific dietary restrictions in the study.

8. SCHEDULE OF EVENTS AND STUDY PARAMETERS

8.1. Schedule of Events

The types and timing of data to be recorded are summarized in Table 2. Please see [Section 8.2](#) for explanations of the study procedures outlined.

Table 2: Schedule of Events

	Screening	Ataluren Treatment						4-Week Follow-Up
Day (± 2)	-28	1 ^a	28	112	196	280	364	392
Weeks	-4	0	4	16	28	40	52/ET ^b	56
Visit	1	2	3	4	5	6	7	8
Informed consent	X							
Clinical and medication history	X							
Vital signs	X	X	X	X	X	X	X	X
Height	X	X	X	X	X	X	X	X
Weight	X	X	X	X	X	X	X	X
Physical examination	X	As clinically indicated						X
Hematology	X	X	X	X	X	X	X	X
Blood sample for gene sequencing ^c	X							
Biochemistry ^d	X	X	X	X	X	X	X	X
Urinalysis	X	X	X	X	X	X	X	X
12-lead ECG	X		X				X	X
Timed function tests		X			X		X	
North Star Ambulatory Assessment		X			X		X	
Blood for ataluren PK ^e		X	X					
Palatability questionnaire			X					
Drug administration		X-----X						
Adverse events		X-----X						X
Concomitant medications	X							X
Non-DMD-related adverse events								X

^a All study and laboratory assessments on the first day of treatment must be done prior to ataluren dosing.

^b Patients who terminate the study early should complete all assessments required for Week 52/ET (Visit 7) and will be required to return 4 weeks from the final dose of study medication for the 4-Week Follow-up Visit.

^c Verification that a blood sample has been drawn for sequencing of the dystrophin gene. A patient who has written documentation of a nonsense mutation as the cause of DMD need not wait for confirmatory results to start study drug as long as the confirmatory blood sample for gene sequencing was drawn.

^d Biochemistry laboratory assessments will include hepatic transaminases and additional parameters as specified in Section 8.2.7.2.

^e On Days 1 and 28, blood samples for PK assessment will be drawn pre-dose and 1 (± 15 min), 2 (± 15 min), 4 (± 30 min), 6 (± 30 min), 8 (± 30 min), and 10 (± 30 min) hours post-dose.

Abbreviations: ECG = electrocardiogram, ET = early termination, PK = pharmacokinetics

8.2. Explanation of Study Procedures

8.2.1. Study Visits

8.2.1.1. Screening (Visit 1)

No study-related procedures should be performed prior to the signing of the informed consent/ assent document(s). Thereafter, patients should undergo the initial set of screening procedures as noted in [Table 2](#).

Study participants will report to the clinic on the morning of each on-site visit and will remain in the clinic until released by the Investigator after all the study-related procedures have been completed and the patient and/or parent(s)/caregiver have been instructed regarding drug storage, reconstitution, and administration.

8.2.1.2. Treatment Visits

During the treatment period, each patient will return to the clinical research facility during Week 0 (Visit 2) and Week 4 (Visit 3) for PK testing, and Week 16 (Visit 4), Week 28 (Visit 5), Week 40 (Visit 6), and Week 52 (Visit 7/ET).

8.2.1.3. End of Treatment

If the patient discontinues treatment prematurely, the procedures required for Week 52 (Visit 7/ET) should be performed before the patient leaves the study and the patient should return for the 4-Week Post-Treatment Follow-up Visit.

Please refer to [Section 10](#) for further details regarding patient withdrawal procedures.

8.2.2. Informed Consent

The Investigator/study staff member must inform each study candidate of the nature of the study, explain the potential risks, and obtain written informed consent from the parent(s)/legal guardian and/or study candidate (as required by local regulations) prior to performing any study-related screening procedures.

8.2.3. Clinical/Medication History

The Investigator or a qualified designee should review the patient's clinical history, including details relating to DMD and any other medical conditions. Information regarding clinical history and current medications must be captured on the medical history and prior/concomitant medication eCRFs, respectively.

8.2.4. Vital Signs

Vital signs (pulse rate and body temperature) will be monitored at all protocol-required study visits. Pulse rate determinations will be performed with the patient in a sitting position after a 5-minute rest.

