4.2. Inclusion Criteria

Patients must meet all of the following conditions to be eligible for enrollment into the study:

General inclusion criteria

1. Evidence of signed and dated informed consent document(s) indicating that the study candidate (and/or a parent/legal guardian) has been informed of all pertinent aspects of the study. *Note: As all study candidates are considered children under local regulation, at least one parent or legal guardian must provide written consent prior to initiation of study-related procedures, in accordance with local regulation, and the study candidate may be required to provide written assent. The rules of the responsible institutional review board/independent ethics committee (IRB/IEC) regarding whether one or both parents must provide consent and the appropriate ages for obtaining consent and assent from the patient should be followed.*
2. Males ≥ 2 to < 5 years of age
3. Body weight ≥ 12 kg
4. Willingness and ability to comply with scheduled visits, drug administration plan, study procedures, and study restrictions.
5. No clinically significant abnormality based upon laboratory assessments during the screening period, in the opinion of the Investigator; good general health, as determined during the screening period by medical history and physical examination (including vital sign measurements).

DMD inclusion criteria

6. Diagnosis of DMD based on an elevated serum CK and genotypic evidence of dystrophinopathy. *Medical documentation of phenotypic evidence of dystrophinopathy needs to be provided upon request by the PTC Therapeutics medical monitor.*
7. Documentation of the presence of a nonsense mutation in at least 1 allele of the dystrophin gene.
8. Verification that a blood sample has been drawn for sequencing of the dystrophin gene. *Note: A patient who has written documentation of a nonsense mutation as the cause of dystrophinopathy need not wait for confirmatory results to start study drug.*

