11.7.3. Vital Signs and ECGs

Vital signs (height, weight, BMI, pulse rate, and body temperature) and ECGs will be listed and summarized by visit. Where appropriate, changes from baseline will be presented by visit.

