12.3. Vital Signs

All vital signs will be taken each visit and include the following parameters:

- Pulse Rate (beats per minute)
- Temperature (°C)
- Respiratory Rate (breaths/min)
- Systolic Blood Pressure (mmHg)
- Diastolic Blood Pressure (mmHg)

Vital signs will be summarized for each clinical assessment using the summary statistics of n, mean, SD, median, and range. These summaries will be presented for the subjects who have data at baseline and the specific follow-up visit. The summarized results will be presented for the 4 week primary PK period of the study and for the extension study data. The organization of the

results is commensurate with the organization of the laboratory data. All subjects in the Safety Population who have a baseline and at least one follow-up vital sign assessment will be included in the presentation of the data. In order for a subject to be included in the analysis for a particular evaluation, the subject must have a baseline value and a follow-up assessment. Unscheduled laboratory evaluations will be presented in the listings. The summarized results will be presented for the 4 week primary PK period of the study and for the extension study data. The results will be presented in Table 14.3.3 entitled *Summary of Vital Sign Results by Visit* (Safety Population). The supportive data listing is Listing 16.2.8.1 entitled *Vital Signs*. This listing will be sorted by subject number, parameter, and relative day.

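### SAP 12.3 plans a by-visit summary of blood pressure and respiratory rate that Protocol 8.2.4 and 11.7.3 do not require sites to measure, so no pre-dose blood pressure baseline is mandated although Protocol 7.1.1 names a possible hypertension risk

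*Protocol*

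**What the plan says.** Protocol 8.2.4 defines the vital signs to be collected: "Vital signs (pulse rate and body temperature) will be monitored at all protocol-required study visits". It adds that pulse is taken with the patient seated after five minutes of rest. Protocol 11.7.3, on analysis, gives a second list: "Vital signs (height, weight, BMI, pulse rate, and body temperature) and ECGs will be listed and summarized by visit". Neither section mentions blood pressure or respiratory rate. The schedule of events (Protocol Table 2, repeated in SAP section 16) marks a vital-signs row at all eight visits but does not name the parameters.

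SAP 12.3 says: "All vital signs will be taken each visit and include the following parameters". It then lists five: pulse rate, temperature, respiratory rate, systolic blood pressure and diastolic blood pressure. The output is Table 14.3.3, "Summary of Vital Sign Results by Visit", limited to subjects with a value at baseline and at the follow-up visit concerned. SAP section 5 defines baseline as the last value before the first dose.

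On why blood pressure might matter, Protocol 7.1.1 says: "Co-administration of systemic corticosteroids with ataluren may cause more frequent instances of hypertension than does systemic corticosteroid use alone". It goes on to say that the blood pressure data so far are not definite about any role of ataluren. The exclusion criteria in Protocol 4.3 do not list corticosteroids, and 7.1.1 lets patients whose steroid treatment changes stay on study drug. Protocol 2.1 notes that steroids are not usually started before age 5.

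**The concern.** The two documents disagree about what is measured, and the protocol is the one that sites follow. A site that does exactly what 8.2.4 asks will record pulse and temperature and nothing else under vital signs. The SAP's blood pressure and respiratory rate summaries would then have no data from that site.

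The missing baseline is the part that cannot be repaired later. Because SAP 12.3 admits only subjects with both a baseline and a follow-up value, and baseline must precede the first dose, a boy whose blood pressure is first taken on treatment cannot enter Table 14.3.3 for that parameter. A raised on-treatment reading could not be compared with a pre-dose one.

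This goes beyond an editorial mismatch because the protocol itself raises a possible blood pressure effect. SAP Table 14.1.5.4 will show which boys received corticosteroids, but there may be no blood pressure data to set beside it. The data monitoring committee's review, once all patients have at least 12 weeks of treatment, would likewise have no protocol-mandated blood pressure data.

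**Working it through.** The plan gives no figure of its own on this point, so the check is a comparison of texts and a count.

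**Parameters by source**

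| Parameter | Protocol 8.2.4 | Protocol 11.7.3 | SAP 12.3 |
|---|---|---|---|
| Pulse rate | yes | yes | yes |
| Body temperature | yes | yes | yes |
| Respiratory rate | no | no | yes |
| Systolic blood pressure | no | no | yes |
| Diastolic blood pressure | no | no | yes |
| Height, weight, BMI | no (height and weight are in 8.2.5) | yes | no |

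SAP parameters without a protocol source: 5 - 2 = 3.

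**Is there another source in the protocol?** The footnotes to Table 2 add no vital-sign parameter. The physical examination in 8.2.5 includes the cardiovascular system at Screening and Visit 8, but does not name blood pressure. The only wording on blood pressure in the protocol is the risk statement in 7.1.1. The omission occurs in both the procedure section and the analysis section, so it is not a slip in one line.

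**Count of readings**

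- Patients: 12 (Protocol 11.1; 5.1 says at least 12, so this is a minimum).
- Visits with a vital-signs mark: 8 (Table 2, Visits 1 to 8).
- Blood pressure readings mandated by the protocol: 0.
- Systolic/diastolic pairs implied by the SAP: 12 x 8 = 96.
- Of these, pre-dose (Screening, and Day 1, where Table 2 requires assessments before dosing): 12 x 2 = 24.
- Post-baseline (Visits 3 to 8): 12 x 6 = 72.
- Check: 24 + 72 = 96.

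The same counts apply to respiratory rate. All of them assume that every boy attends every visit, so dropouts would lower them.

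**The case against.** Several stronger conclusions are tempting, and the documents do not support them.

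- **That blood pressure will go unscreened and unmeasured.** The SAP says it is taken, and the eCRF and study manual are not available here. The documents support only that the protocol does not require it.
- **That inclusion criterion 5 lacks data.** The criterion refers to vital sign measurements and 8.2.4 defines them, so pulse and temperature satisfy it. No criterion mentions blood pressure. Screening also includes clinical history and a full physical examination, and exclusion criterion 3 leaves room for the investigator's judgement.
- **That a primary endpoint loses its source.** The primary objective rests on adverse events, laboratory abnormalities and ECGs, and Protocol 3.3 does not name vital signs. Hypertension that needs intervention or further investigation would still be reportable as an adverse event under 9.1.1. What remains is that detection would depend on unscheduled readings.
- **That the safety table would contain empty rows.** SAP section 5 prints a row only if at least one subject has data, so the rows would not appear at all.
- **That the omission is what prevents an answer on hypertension.** The question in 7.1.1 compares ataluren plus corticosteroid with corticosteroid alone. A single-arm study of about 12 boys has no such comparison, and the planned natural-history extract (SAP 3.9) covers demographics, timed function tests and NSAA. Scheduled readings would describe blood pressure but would not attribute it.

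The best argument on the other side is that the SAP may be the document in error. It contains other wording that does not fit this study: references to active or placebo drug in section 5, and limits for ACTH and urine protein ratios in 12.2, which Protocol 8.2.7 does not collect. The blood pressure rows could also be carried over, and deleting them would remove the contradiction. That is fair, and the documents do not settle which list was intended. But deletion would leave a risk that the protocol names with no scheduled data, where a reading at visits already planned costs little.

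**Conclusion.** The contradiction is real and should be fixed. Three of the five vital-sign parameters in SAP 12.3 have no protocol source, and the protocol mandates none of the 96 blood pressure pairs that the SAP implies for 12 boys over 8 visits. If sites follow the protocol as written, the planned blood pressure summary has no data and the pre-dose baseline cannot be recovered.

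The conclusion rests on the text alone; if the eCRF already captures blood pressure at Screening or pre-dose on Day 1, the practical loss is smaller and the repair is mainly one of wording. The hypertension risk is hedged in the protocol and applies only with systemic corticosteroids. The number of boys exposed to it may therefore be small, but they are not excluded. The point does not invalidate eligibility or the primary endpoints.

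**What to change.** Reconcile Protocol 8.2.4, 11.7.3 and Table 2 with SAP 12.3, so that one list of vital signs governs both collection and analysis. The preferred route is to add systolic and diastolic blood pressure and respiratory rate to 8.2.4 at the visits already marked for vital signs, including Screening and pre-dose Day 1, with the patient seated after the five-minute rest already specified for pulse. Add the same parameters to 11.7.3, and name them in a footnote to Table 2. If the sponsor decides not to collect them, remove them from SAP 12.3 and state that blood pressure is assessed only through adverse event reporting. The SAP should also say how on-treatment readings without a pre-dose value will be shown.

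The cost is a short amendment, additional eCRF fields and a few minutes at each existing visit, with no new visits or blood draws. Some readings in boys aged 2 to under 5 will be missing. No clinical threshold or treatment rule is proposed.
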